4. EVALUATION CRITERIA

The Clinical Global Impression Scale (see *Annex I*) will be used to provide a rating of illness severity, improvement and response to treatment.

4.1. SAFETY ASSESSMENT

Safety of Brexpiprazole (Rexulti™) Film-coated Tablet will be evaluated based on the reported AEs per assessment.

4.2. EFFICACY ASSESSMENT

Efficacy of Brexpiprazole (Rexulti™) Film-coated Tablet will be evaluated using:

1. Clinical Global Impression-Severity (CGI-S) Scale:
 - Numbers and proportions of responders (defined as patients with CGI severity (CGI-S) score of 1 (normal, not at all ill), 2 (borderline mentally ill), 3 (mildly ill), 4 (moderately ill), 5 (markedly ill), 6 (severely ill), 7 (among the most extremely ill patients))
2. Efficacy will be evaluated using Clinical Global Impression-Improvement (CGI-I) Scale:
 - Numbers and proportions of responders (defined as patients with CGI improvement (CGI-I) score of 1 (very much improved), 2 (much improved), 3 (minimally improved), 4 (no change), 5 (minimally worse), 6 (much worse), 7 (very much worse))

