Treatment Indication(s)	
 • For the treatment of schizophrenia. • Adjunctive therapy to antidepressants for the treatment of major depressive disorder (MDD) 		
Objective(s)	To provide post marketing surveillance data on the safety and efficacy of Brexpiprazole (Rexulti™) Film-coated Tablet for schizophrenia and adjunctive therapy of major depressive disorder (MDD) in the Philippines.		
Study Design			
Center	Multi-center		
Blinding	Open		
Control	Active		
Design	Single Group		
Subject Population			
Planned # of subject	A total of 300 subjects will be included in the trial.		
Gender	Male and Female		
Age range	Adults (18 years old and above)		
Healthy subjects or treatment condition	Treatment condition		
Test Product, Dose, Mode of Administration			
Brand name (API)	Rexulti™	Administration route	Per Orem (PO)
Dosage form	Film-coated Tablet	Dose, regimen	Once a day
Criteria for Evaluation			
Primary Outcome Variables	Safety Assessment: Safety of Brexpiprazole (Rexulti™) Film-coated Tablet will be evaluated based on the reported AE's per assessment.		
Secondary Outcome Variables	Efficacy Assessment: Efficacy of Brexpiprazole (Rexulti™) Film-coated Tablet will be evaluated using the Clinical Global Impression (CGI) Scale : CGI – Severity - Numbers and proportions of responders (defined as patients with CGI severity (CGI-S) score of 1 (normal, not at all ill), 2 (borderline mentally ill), 3 (mildly ill), 4 (moderately ill), 5 (markedly ill), 6 (severely ill), 7 (among the most extremely ill patients)) CGI – Improvement - Numbers and proportions of responders (defined as patients with CGI improvement (CGI-I) score of 1 (very much improved), 2 (much improved), 3 (minimally improved), 4 (no change), 5 (minimally worse), 6 (much worse), 7 (very much worse))		
Study Duration			
Treatment duration	8 weeks		
Further Study Details			
Assessments will be done upon initiation, (Baseline visit), 4 weeks later (Visit 2), until completion of the study week 8 (Study Completion). Demographic information and vital signs will be collected.			

INTRODUCTION

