2.2. PROCEDURES

Based on his clinical decision, the attending physician will enroll patients with schizophrenia and MDD to the program. The attending physician will explain to the patient or his legal guardian the purpose of the PMS and will obtain the patient or legal guardian's consent that Brexpiprazole (Rexulti™) Film-coated Tablet will be administered.

Data on the safety aspects of Brexpiprazole (Rexulti™) Film-coated Tablet will be collected in terms of adverse events. Efficacy will be measured using the Clinical Global Impression (CGI) Scale:

CGI-Severity

- Numbers and proportions of responders (defined as patients with CGI severity (CGI-S) score of 1 (normal, not at all ill), 2 (borderline mentally ill), 3 (mildly ill), 4 (moderately ill), 5 (markedly ill), 6 (severely ill), 7 (among the most extremely ill patients))

CGI-Improvement

- Numbers and proportions of responders (defined as patients with CGI improvement (CGI-I) score of 1 (very much improved), 2 (much improved), 3 (minimally improved), 4 (no change), 5 (minimally worse), 6 (much worse), 7 (very much worse) after the first and last Brexpiprazole (Rexulti™) Film-coated Tablet dose. Assessments will be done upon initiation, (Baseline visit), and 4 weeks later (Visit 2), until completion of the study week 8 (Study completion). Demographic information and vital signs will be collected.

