5. STATISTICAL ANALYSIS

Analysis of data will be limited to descriptive statistics only. Safety will be evaluated based on the reported AEs per assessment. Efficacy will be evaluated using the Clinical Global Impression-Severity (CGI-S) and Clinical Global Impression-Improvement (CGI-I) Scales to monitor severity and improvement from mean baseline score (before initial dose) up to the last assessment (Week 8 – Study Completion).

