ANNEX I
ASSESSMENT CRITERIA

i. Safety

- All adverse events will be collected on Visit 1 and Study Completion. See Annex III for other safety information.

ii. Efficacy

Baseline visit (Day 0):

Clinical Global Impression - Severity of Illness	
[1] Normal, not at all ill	[5] Markedly ill
[2] Borderline mentally ill	[6] Severely ill
[3] Mildly ill	[7] Among the most extremely ill patients
[4] Moderately ill	

Visit 1 (after 4 weeks) and Study Completion (after 8 weeks):

Clinical Global Impression - Severity of Illness	
[1] Normal, not at all ill	[5] Markedly ill
[2] Borderline mentally ill	[6] Severely ill
[3] Mildly ill	[7] Among the most extremely ill patients
[4] Moderately ill	
Clinical Global Impression - Improvement	
[1] Very much improved	[5] Minimally worse
[2] Much improved	[6] Much worse
[3] Minimally improved	[7] Very much worse
[4] No change	

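### CGI-S and CGI-I responders are defined as patients scoring 1 to 7, the whole of each scale, so every rated patient is a responder

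*Protocol*

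**What the plan says.** The Protocol synopsis names reported adverse events as the primary outcome, and the CGI responder numbers and proportions as the secondary ones. No other secondary outcome is listed.

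- **CGI-S.** In the synopsis, responders are "defined as patients with CGI severity (CGI-S) score of 1 (normal, not at all ill), 2 (borderline mentally ill), 3 (mildly ill" and so on up the scale. Section 2.2 shows where the list ends: "5 (markedly ill), 6 (severely ill), 7 (among the most extremely ill patients".
- **CGI-I.** Section 4.2 counts "responders (defined as patients with CGI improvement (CGI-I) score of 1 (very much improved), 2 (much improved), 3 (minimally improved), 4 (no change), 5", and its list closes with "4 (no change), 5 (minimally worse), 6 (much worse), 7 (very much worse". Section 2.2 has the same list and adds a timing phrase: "6 (much worse), 7 (very much worse) after the first and last Brexpiprazole" dose.
- **Purpose.** Section 4 says that the CGI "will be used to provide a rating of illness severity, improvement and response to treatment".
- **Analysis.** Section 5 limits the analysis to descriptive statistics. It uses both scales "to monitor severity and improvement from mean baseline score (before initial dose) up to the last assessment", which is Week 8.
- **Rating forms.** Annex I prints seven categories, 1 to 7, for each scale. CGI-S is rated at baseline, 4 weeks and 8 weeks; CGI-I is rated at 4 and 8 weeks only.

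No section gives a narrower responder threshold for either scale.

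**The concern.** A responder definition has to divide patients into those who responded and those who did not. This one leaves nobody in the second group. A patient rated at the worst end of CGI-I counts as a responder, and so does a patient at the most severe level of CGI-S. On CGI-S a patient already qualifies at the baseline rating, before the first dose.

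The stated objective covers efficacy as well as safety, and section 4 gives the CGI the task of rating response. If the definition is followed exactly, the reported efficacy outcome is 100% of rated patients whatever the drug does. In an open, single-group study there is no control group against which such a figure could be recognised as empty.

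There is a second consequence. If the problem is noticed only at analysis, someone will have to choose a cut-off with open-label ratings already in view.

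**Working it through.** The Protocol states no expected responder rate, effect size or power, so there is no figure to reproduce. The check compares the responder lists with the scales and then asks whether the resulting proportion can vary.

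**Inputs**

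- CGI-S responder scores (synopsis, 2.2, 4.2): {1, 2, 3, 4, 5, 6, 7}
- CGI-I responder scores (same places): {1, 2, 3, 4, 5, 6, 7}
- CGI-S and CGI-I categories on the forms (Annex I): {1, 2, 3, 4, 5, 6, 7} each
- Planned number of patients (synopsis, 2.1): 300

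**Step 1: scores that are not a response.** Scale minus responder list = {1,…,7} − {1,…,7} = empty set, for both scales.

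**Step 2: what the CGI-I list contains.** Scores 1 to 3 are improvement (3 categories), 4 is no change (1) and 5 to 7 are worsening (3). So (1 + 3)/7 = 4 of the 7 counted categories are not improvement.

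**Step 3: the proportion.** With n rated patients, responders/rated = n/n = 100% for any n up to 300.

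**Step 4: does it respond to the data?** The table takes 300 rated patients under three patterns of CGI-I scores. The last two columns use cut-offs that are *not* in the Protocol; they are there only to show how a proper subset behaves.

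| CGI-I scores | As written (1–7) | Illustration: 1–2 | Illustration: 1–3 |
|---|---|---|---|
| All rated 1 | 300/300 = 100% | 100% | 100% |
| All rated 7 | 300/300 = 100% | 0% | 0% |
| Spread evenly over 1–7 (expected) | 7/7 = 100% | 2/7 = 28.6% | 3/7 = 42.9% |

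The column for the written definition is constant.

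**Step 5: a different denominator does not help.** If all 300 enrolled patients were the denominator, the figure would be the share who have a rating. Assuming 10% to 30% are unrated (the Protocol gives no such figure), it would run from 270/300 = 90% down to 210/300 = 70%. That measures completeness of follow-up, and is still unrelated to improvement.

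**The case against.** The best defence is that the authors meant a frequency table. Each score is listed with its own label, under a heading of numbers and proportions, in a purely descriptive plan; nobody would normally write out seven labels to define a single group. On that reading nothing is lost, because any cut-off can be read from the table. This may well be the intent. But the text defines responders and does so three times, so under this reading that word is wrong in all three places and response to treatment is still not defined. The wording has to change either way.

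A second defence is that a statistical analysis plan, not shown here, could settle the matter. It could add detail, but this is not a gap left for it to fill. The Protocol fixes a definition, and an analysis plan with a usable cut-off would contradict it.

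Third, section 5 already provides a description from baseline to Week 8. That stands, and it limits the harm. It does not supply a responder definition or repair the named secondary outcomes.

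A side point concerns timing. The synopsis and 4.2 attach no visit to the responder definition, and the phrase in 2.2 about the first and last dose does not match Annex I well, which rates CGI-I only at 4 and 8 weeks. This is minor: the visit schedule is clear from 2.2, section 5 and Annex I, and the choice of visit for the headline figure could be left to an analysis plan.

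**Conclusion.** The concern holds. As written, 7 of 7 categories on each scale count as response, and both secondary responder proportions equal 100% of rated patients for any set of scores. This follows from the Protocol's own lists and rating forms and needs no assumption. Only the 70% to 90% range for an all-enrolled denominator rests on an assumed share of unrated patients.

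The weight is moderate. The outcomes are secondary and descriptive, no sample size or test depends on them, safety is primary, and the individual CGI ratings remain usable. It should be fixed because following the Protocol exactly produces an efficacy figure without meaning.

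**What to change.** Make the same change in the synopsis, section 2.2 and section 4.2:

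1. Present the 1 to 7 lists as the number and proportion of patients in each category at each visit, and remove the word responders from them.
2. If a responder rate is to be kept, define it as a proper subset of CGI-I at a named visit. A score of 1 or 2 at Week 8 is one example; the Protocol offers no cut-off, so the sponsor must confirm the choice.
3. For CGI-S, replace the responder with each patient's change from baseline to Week 8, in line with section 5. Relabelling under item 1 is the minimum.

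No new data are needed: Annex II shows that the case report form already records CGI-S before the initial dose and both scales at 4 and 8 weeks. The visible cost is that a reported responder rate will fall below 100%.

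Timing is the less obvious cost. Section 6 estimates data collection from February 2020 and an interim statistical report in Q2 2022. A cut-off introduced after open-label ratings have been seen could be chosen to suit them, so the amendment should be dated and should state what data had been reviewed. Relabelling alone does not carry that risk.

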5. STATISTICAL ANALYSIS

Analysis of data will be limited to descriptive statistics only. Safety will be evaluated based on the reported AEs per assessment. Efficacy will be evaluated using the Clinical Global Impression-Severity (CGI-S) and Clinical Global Impression-Improvement (CGI-I) Scales to monitor severity and improvement from mean baseline score (before initial dose) up to the last assessment (Week 8 – Study Completion).

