	CGI-S score before the initial dose	
 • To write the corresponding scale
	CGI-I and CGI-S score of Illness 4 weeks after initial dosing (Baseline)	
 • To write the corresponding scale
	CGI-I and CGI-S score of Illness 8 weeks after initial dosing (Baseline)	
 • To write the corresponding scale
	Discontinuation section	
 • Tick/check appropriate box
	Investigator name, signature and date	
 • To be signed by the Investigator/ Physician
BASELINE	Vital signs	
 • Weight of the patient (in kg) • Patient's blood pressure (BP) • Patient's heart rate (HR) • Patient's respiratory rate (RR) • Patient's temperature (in Celsius)
	Psychotropic medications	
 • Tick/check appropriate box
	CGI-S score before the initial dose	
 • To write the corresponding scale
VISIT 2 & STUDY COMPLETION	Adverse Events	
 • Tick/check appropriate box • List all AE and indicate severity of event by putting a tick on the appropriate box.
	CGI-I and CGI-S score of illness 8 weeks after initial dosing (Baseline)	
 • Please encircle the corresponding score

HANDLING AND CARE OF THE COMPLETED CRFs

Once the patient has completed the PMS or has been prematurely discontinued from the PMS, the physician can submit the CRFs of these patients to the PSR. The PSR checks the CRF for completeness and legibility and submits the CRF to Medical Affairs (MA). MA collates the CRF and submits clear copies to Data Management for encoding and analysis.

To minimize delay in encoding and analysis, the PSR should carefully check the completed CRF before submitting MA. Queries from the Data Management should be forwarded to MA who will check the CRFs. All the copies of the CRFs will be collected back in the event that an entry on the CRF needs to be edited.

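### No CGI rating is listed at early discontinuation, so a Week 8 efficacy summary may represent completers only

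*Protocol*

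**What the plan says.** The synopsis plans a single-group surveillance: "A total of 300 subjects will be included in the trial". Safety is primary and the CGI outcomes are secondary.

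The points that bear on the CGI ratings are these:

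- **Baseline.** Annex II lists a "CGI-S score before the initial dose", and Annex I places CGI-S at Day 0.
- **After baseline.** Annex I lists CGI-S and CGI-I at "Visit 1 (after 4 weeks) and Study Completion (after 8 weeks". Annex II gives the same two times. Section 2.2 and Annex II call the 4-week visit Visit 2; it is the same visit.
- **Early leaving.** The CRF instructions in Annex II include a treatment completion field and a separate discontinuation section. CRFs are handed in "Once the patient has completed the PMS or has been prematurely discontinued from the PMS", and then go on for encoding and analysis. No CGI rating is listed for the time of discontinuation.
- **Time frame of the analysis.** Section 5 says "Analysis of data will be limited to descriptive statistics only" and describes the CGI scales from baseline "up to the last assessment (Week 8 – Study Completion".
- **Time frame in the procedures.** Section 2.2, in its CGI-I item, places response "after the first and last Brexpiprazole (Rexulti™) Film-coated Tablet dose".
- **Outcome.** Section 4.2 asks for "Numbers and proportions of responders" on each scale and lists every score from 1 to 7 in the definition.

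**The concern.** The CGI is the only efficacy measure, and there is no second arm against which selective loss could be seen. If the last assessment is the Week 8 visit and nobody is rated on leaving early, the final CGI summary can contain only patients who reached Week 8. Whether those patients did better or worse than the rest cannot be learned from the ratings collected.

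This belongs in the protocol. An analysis plan can choose a denominator and a rule for missing values, but it cannot supply a rating that nobody was asked to make. The visit schedule and the CRF instructions are fixed here.

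**Working it through.** **Step 1. Which ratings exist, by time of leaving the surveillance.** This follows from Annexes I and II.

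| Patient leaves | Scheduled CGI ratings | Contributes at Week 8 |
|---|---|---|
| Before Week 4 | Baseline CGI-S only | No |
| Between Weeks 4 and 8 | Baseline CGI-S; Week 4 CGI-S and CGI-I | No |
| Not before Week 8 | All of the above; Week 8 CGI-S and CGI-I | Yes |

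**Step 2. Section 2.2 beside Section 5.** Section 2.2 ties response to the last dose. Section 5 ties the last assessment to Week 8. For a patient who completes, the two nearly coincide. For one who leaves at, say, Week 6, Section 2.2 calls for a rating that the annexes do not schedule, and Section 5 points to a visit that may not happen.

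**Step 3. Possible size for a response proportion.** There is no plan figure to reproduce. The 300 has no stated basis, and the protocol gives no rate of leaving and no response rate. Let *d* be the share leaving without a final rating, *p* the response among completers and *q* the unobserved response among leavers.

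- Response over all = *p*(1 − *d*) + *qd*
- Completer figure minus overall figure = *d*(*p* − *q*)

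The completer figure is too high if *q* < *p* and too low if *q* > *p*. The limits are *q* = 0 and *q* = 1. With *p* = 60% (assumed) and 300 patients:

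| *d* (assumed) | Completers | Responders among them | Overall, *q* = 0 | Overall, *q* = 1 |
|---|---|---|---|---|
| 10% | 270 | 162 | 162/300 = 54% | 192/300 = 64% |
| 20% | 240 | 144 | 144/300 = 48% | 204/300 = 68% |
| 30% | 210 | 126 | 126/300 = 42% | 216/300 = 72% |
| 40% | 180 | 108 | 108/300 = 36% | 228/300 = 76% |

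For *p* from 50% to 70% and *d* from 10% to 40%, the completer figure exceeds the lower limit by *pd*. That is 0.5 × 0.1 = 5 points up to 0.7 × 0.4 = 28 points. It falls short of the upper limit by (1 − *p*)*d*, which is 0.3 × 0.1 = 3 points up to 0.5 × 0.4 = 20 points.

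These figures presuppose a responder cut-off. Under the present definition every rated patient falls within scores 1 to 7, so the proportion among rated patients would be 100% whatever happened.

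**Step 4. Possible size for mean CGI-S, which needs no cut-off.** All values here are assumed: 240 completers go from 4.5 to 3.5, and 60 leavers start at 5.0.

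- Change in completers: 4.5 − 3.5 = 1.0.
- Baseline mean of all 300: (240 × 4.5 + 60 × 5.0)/300 = 4.6. Set against the completers' Week 8 mean, this gives 4.6 − 3.5 = 1.1. Section 5 refers to the mean baseline score without saying whose.
- Change over all 300 if leavers did not change: (240 × 1.0 + 60 × 0)/300 = 0.8.
- Change over all 300 if leavers improved by 2.0: (240 × 1.0 + 60 × 2.0)/300 = 1.2.

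**Step 5. What a rating at discontinuation would buy.** For response at the last assessment, the distance between the limits equals the unrated share. With 60 of 300 unrated it is 20 points. If 40 of those 60 were rated on leaving (assumed), it would be 20/300 = 6.7 points.

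**The case against.** A reader might infer that the protocol restricts the efficacy analysis to completers. It does not say so. Section 5 names no denominator or analysis set, and its wording describes a course over time that includes Week 4. Annex II collects the CRFs of patients who leave early and sends them on for analysis, so anyone who reached Week 4 has usable ratings. Denominators, analysis sets and missing-data rules are commonly left to a statistical analysis plan, which is not at hand; their absence is no finding. All of this stands.

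A reader might also infer that the result must be too favourable because patients stop for lack of effect or intolerance. No passage says why patients would leave. Improvement, cost or loss to follow-up are possible too, and the limits in the working lie on both sides of the completer figure. This also stands.

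Two further cautions are fair. The CRF pages are not reproduced, so one can say only that no CGI rating is listed at discontinuation, not that none is ever made. And stopping the tablet is not the same as leaving the surveillance: the CRF records treatment completion and discontinuation in separate places, and nothing says that a patient off treatment misses the Week 8 visit.

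Finally, efficacy is secondary and the analysis is descriptive, with no test or threshold at stake. That limits the weight of the point. It does not remove the gap in the schedule, which no analysis rule can fill.

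**Conclusion.** The point holds as a gap in data collection. Post-baseline CGI ratings are scheduled at Weeks 4 and 8 only, Section 5 equates the last assessment with Week 8, and none of the instructions shown asks for a rating when a patient leaves early. A Week 8 summary may therefore represent completers only, and Sections 2.2 and 5 describe the final time point differently.

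The documents fix neither the size nor the direction of any bias. With 60% response among completers and 20% leaving early, both assumed, response over all 300 could lie anywhere from 48% to 68%. That range takes leavers to have no usable final rating; Week 4 ratings would narrow it for those who reached that visit, if a last-available rule were used. The documents do not support the stronger statement that the reported response is that of completers by rule, or that it is inflated.

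**What to change.** - **Annexes I and II:** have the existing Study Completion CGI-S and CGI-I page completed at the time of discontinuation for any patient who leaves early and can be assessed.
- **Section 5:** define the last assessment as Week 8 or, for early leavers, the discontinuation rating. State the number rated out of all treated beside each CGI summary.
- **Section 2.2:** reconcile its reference to the last dose with that definition.

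The cost is about one line in each place and one short additional rating for early leavers. It cannot be obtained from patients lost to follow-up, and the response figure may come out less favourable. A rating on leaving describes the patient at that time and not at Week 8, so the two kinds should be identifiable in the tables.

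Whether early leavers count as non-responders can be left to the analysis plan. That choice has meaning only once a responder cut-off is fixed, because the current definition lists every score.
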